2.3.4 Safety Endpoints

The safety endpoints include the following:

- Safety and tolerability profile of obicetrapib assessed by AEs, ESIs, vital signs (including blood pressure as assessed by office blood pressure measurements), ECG, and clinical laboratory values, and
- Assessment of ABPM measured at Baseline and at Day 270.

3 STATISTICAL METHODOLOGY

3.1 General Considerations

3.1.1 Analysis Day

Analysis day will be calculated from the date of first dose of study drug. The day of the first dose of study drug will be Day 1, and the day immediately before Day 1 will be Day -1. There will be no Day 0.

3.1.2 Analysis Visits

Scheduled visits will be assigned to analysis visits as recorded on the CRF.

For each analysis visit, if a scheduled visit occurs within the analysis day window, then the measurement from this scheduled visit will be used. If no scheduled visit occurs or laboratory results of the scheduled visit were unreportable, the unscheduled measurement closest to the target day will be used. If measurements are equidistant to the target day, the later measurement will be used. Otherwise, unscheduled visits will not be re-assigned and will remain labelled as unscheduled. If laboratory measurements for the scheduled visit were taken while a participant was not in a fasting state and laboratory measurements are available from an unscheduled visit

during which the participant was in a fasting state (and the visit occurred within seven days of the scheduled visit), those fasted labs will be utilized in place of the unfasted labs.

Early termination (ET) visits will be assigned to analysis visits according to the visit windows in Table 2 and Table 3.

Table 2 Analysis Visit Windows (excluding Japan)

Analysis Visit	Target Analysis Day	Low Analysis Day	High Analysis Day
Day 1 (Visit 2)	1	NA	NA
Day 30 (Visit 3)	30	2	57
Day 84 (Visit 4)	84	58	132
Day 180 (Visit 5)	180	133	225
Day 270 (Visit 6)	270	226	317
Day 365 (EOT/Visit 7)	365	318	N/A

Table 3 Analysis Visit Windows (Japan Only)

Analysis Visit	Target Analysis Day	Low Analysis Day	High Analysis Day
Day 1 (Visit 2)	1	NA	NA
Day 14 (Visit 3)	14	2	22
Day 30 (Visit 4)	30	23	57
Day 84 (Visit 5)	84	58	132
Day 180 (Visit 6)	180	133	225
Day 270 (Visit 7)	270	226	317
Day 365 (EOT/Visit 8)	365	318	N/A

3.1.3 Handling of missed/delayed visits dues to COVID-19

Due to the pandemic of Coronavirus Disease 2019 (COVID-19), study visits for some participants may be partially completed, delayed, or cancelled, with the corresponding information collected on the CRF. The sites could do the following:

- If the visit window is exceeded by more than 7 days for the Visit 3 (Day 30) assessment, the visit may be recorded as an unscheduled visit.
- If the visit window is exceeded by more than 14 days for Visit 4 (Day 84), Visit 5 (Day 180), Visit 6 (Day 270), or Visit 7 (Day 365); then the visit may be recorded as an unscheduled visit.

3.1.4 Definition of Baseline

Baseline is defined as the last measurement prior to the first dose of study drug, unless otherwise stated.

3.1.5 Summary Statistics

Categorical data will generally be summarized with counts and percentages of subjects. The denominator used for the percentage calculation will be clearly defined. Continuous data will generally be summarized with descriptive statistics including n (number of non-missing values), mean, median, standard deviation, 1st and 3rd quartiles, minimum, and maximum.

3.1.6 Hypothesis Testing

The hypothesis testing of the percentage change in LDL-C from Baseline to Day 84 is statistically defined as:

$$H_0: \mu_1 - \mu_0 = 0, H_1: \mu_1 - \mu_0 \neq 0,$$

where μ_0 - the percentage change in LDL-C in the placebo group,

μ_1 - the percentage change in LDL-C in the obicetrapib group.

A fixed sequential testing procedure will be implemented in order to control the Type I error rate. In a hierarchical step-down manner, the primary endpoint will be tested first, followed by the secondary efficacy endpoints in a pre-specified order (see [Section 3.4.2](#)). No adjustment for multiple comparison will be made for the exploratory efficacy endpoints.

The hypothesis testing of the change in average systolic blood pressure (SBP) measured by 24-hour ABPM from Baseline to Day 270 is defined as follows:

$$H_0: \mu_T - \mu_P \geq 3 \text{ mmHg}, H_1: \mu_T - \mu_P < 3 \text{ mmHg}$$

where μ_P - the change in average SBP in the placebo group,

μ_T - the change in average SBP in the obicetrapib group.

3.1.7 Evaluation of Site Effect

This is a multi-center study. Sites will not be pooled for any planned inferential analysis but may be pooled for subgroup analysis to assess the heterogeneity of treatment effects among pooled sites. The final pooling algorithm, if needed, will be specified before treatment unblinding and will be provided as an addendum to the SAP. Additionally, a review of by-site effects will be performed in the context of data listing review.

3.1.8 Handling of Dropouts and Missing Data

The objective is for missing data to be kept to a minimum. Continued efforts will be made to measure endpoints on all subjects, including those who may have discontinued study drug. Accordingly, site investigators have been robustly trained about the importance of participant retention and multiple approaches will be implemented to retain participants who fail to actively maintain contact with the investigator.

Date Values

In cases of incomplete dates (e.g., AE, concomitant medication, and medical history start and/or stop dates), the missing component(s) will be assumed as the most conservative value possible. For example, if the start date is incomplete, the first day of the month will be imputed for the missing day and January will be imputed for the missing month. If a stop date is incomplete, the last day of the month will be imputed for the missing day and December will be imputed for the missing month. Incomplete start and stop dates will be listed as collected without imputation.

Date imputation will only be used for computational purposes such as treatment-emergent status. Actual date values, as they appear in the original CRFs, will be presented within the data listings.

Non-Data Values

For sensitivity analyses of the primary efficacy endpoint, missing values will be imputed using multiple imputation methods (see [Section 3.4.1](#)). For the analyses of secondary and exploratory efficacy endpoints, no imputation will be made for missing values. Safety data will be used according to availability, with no imputation for missing data.

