#### 8.2 Adverse Events

An AE is defined as any untoward medical occurrence in a clinical investigation participant administered a pharmaceutical product, which does not necessarily have a causal relationship with this treatment. An AE can therefore be any unfavorable and/or unintended sign (including an abnormal laboratory finding), symptom, or disease temporally associated with the use of an investigational medicinal product, whether or not related to the investigational medicinal product. All AEs, including observed or volunteered problems, complaints, or symptoms, are to be recorded on the appropriate eCRF.

AEs, which include clinical laboratory test variables, will be monitored and documented from the time of signing of informed consent at Screening (Visit 1) until the EOS Visit (35 days after the EOT Visit). Participants should be instructed to report any AE that they experience to the Investigator, whether or not they think the event is due to study treatment. Beginning at the time of signing of informed consent, Investigators should make an assessment for AEs at each visit and record the event on the appropriate AE eCRF.

Wherever possible, a specific disease or syndrome rather than individual associated signs and symptoms should be identified by the Investigator and recorded on the eCRF. However, if an observed or reported sign or symptom is not considered a component of a specific disease or syndrome by the Investigator, it should be recorded as a separate AE on the AE eCRF. Additionally, the condition that led to a medical or surgical procedure (eg, surgery, endoscopy, tooth extraction, or transfusion) should be recorded as an AE, not the procedure itself.

Any medical condition already present at Screening (Visit 1) should be recorded as medical history and not be reported as an AE unless the medical condition or signs or symptoms present at Baseline changes in severity, frequency, or seriousness at any time during the study. In this case, it should be reported as an AE.

Clinically significant abnormal laboratory or other examination (eg, ECG) findings that are detected during the study or are present at Screening (Visit 1) and significantly worsen during the

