#### 10.1.5 Data Validation

Validation checks programmed within the EDC system, as well as supplemental validation performed via review of the downloaded data, will be applied to the data in order to ensure accurate, consistent, and reliable data. Data identified as erroneous, or data that are missing, will be referred to the study site for resolution through data queries.

The eCRFs must be reviewed and electronically signed by the Investigator.

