3.5.1 Adverse Events (AEs)

AEs will be categorized by primary system organ class and preferred term as coded using the current MedDRA version category designation.

An overview of treatment-emergent AEs (TEAEs) will be provided including counts and percentages of participants with the following:

- Any TEAEs (overall and by maximum severity)
- Any TEAEs (non-serious)
- Any study drug related TEAEs (overall and by maximum severity)
- Any TEAEs leading to discontinuation of study drug
- Any treatment-emergent serious AEs (TESAEs)

- Any study drug related TESAEs
- Any TEAEs leading to death.

The TEAEs described above will be summarized separately by system organ class and preferred term. The non-serious TEAEs occurring in more than 2% of participants in any treatment group and preferred term will be summarized.

Listings will be presented specifically for TEAES, TESAEs, TEAEs leading to discontinuation of study drug and TEAEs leading to death.

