7 PROGRAMMING SPECIFICATIONS

Analyses will be performed using SAS® version 9.4 or higher. All available data will be presented in subject data listings which will be sorted by subject and visit date as applicable. Detailed Programming Specifications will be provided in a separate document.

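### Incomplete AE start dates are set to the 1st of the month or to January with no floor at first dose, so AEs that began after dosing can drop out of the TEAE tables; TEAE itself is not defined

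*SAP*

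**What the plan says.** SAP 3.1.8 (Date Values) has one rule for incomplete AE, concomitant medication and medical history dates. Its principle is that "the missing component(s) will be assumed as the most conservative value possible". Its only worked instruction for starts is that "if the start date is incomplete, the first day of the month will be imputed for the missing day and January will be imputed" for a missing month; stops go to the end of the month or to December. On purpose, it says: "Date imputation will only be used for computational purposes such as treatment-emergent status". A wholly missing start date is not covered.

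SAP 3.1.1 makes the day of first dose Day 1. No section compares an imputed start date with it.

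SAP 3.5.1 rests on treatment-emergent events: "An overview of treatment-emergent AEs (TEAEs) will be provided including counts and percentages of participants with the following". The tables by system organ class and preferred term use the same set, and so do the named listings: "Listings will be presented specifically for TEAES, TESAEs, TEAEs leading to discontinuation of study drug and TEAEs leading to death". The abbreviation list expands TEAE, but neither the SAP nor Protocol 8.2 and 9.2.2 defines it.

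**The concern.** Protocol 8.2 collects AEs from consent onward, and the screening period is Day -28 to Day -1. Pre-dose and post-dose AEs are therefore in one dataset, and the start date alone separates them. For medical history or prior medication, moving an unknown start earlier is a sensible default. For an AE close to first dose it moves a post-dose event into screening and out of the safety tables. That is the opposite of conservative, which is the aim the same section states.

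The events at risk when the day is missing all start in the calendar month of first dose, which is where start-of-treatment tolerability is read. There is also a knock-on in SAP 3.5.2. The blood-pressure ESI requires a hypertension AE after Baseline and a medication change within 30 days of its start, so a back-dated start can break that link too.

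**Working it through.** The plan gives no figure to reproduce. The check applies the written rule literally and counts how often it moves a post-dose onset before first dose.

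**Worked dates, first dose 20 June 2022 (illustrative)**
- True onset 25 June, day missing: imputed 1 June, Day -19, not treatment-emergent.
- True onset 15 October, day and month missing: imputed 1 January, Day -170, not treatment-emergent.
- True onset 10 July, day missing: imputed 1 July, Day 12, still treatment-emergent.

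The error needs the partial date to share the month (day missing) or the year (month missing) of first dose.

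**Inputs.** 365 treatment days plus 35 days of follow-up (SAP 2.2.1) give a 400-day window; a 365-day window is also shown. Assumptions: first dose uniform over a 365-day year, onset uniform over the window with the dosing day included, and a TEAE is an AE with onset on or after first dose.

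**Day missing.** In a month of length L with first dose on day k > 1, every onset from day k to day L is lost, that is L - k + 1 days. Summed over k = 2 to L this is L(L - 1)/2: 465 for 31 days, 435 for 30, 378 for 28. Over the year: 7 × 465 + 4 × 435 + 378 = 5,373. For the 14-day window each term is capped at 14, giving 329, 315 and 287 per month: 7 × 329 + 4 × 315 + 287 = 3,850.

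| Onset window from first dose | Lost / all pairs | Share |
|---|---|---|
| 14 days | 3,850 / (365 × 14 = 5,110) | 75.3% |
| 30 days | 5,373 / (365 × 30 = 10,950) | 49.1% |
| 84 days | 5,373 / (365 × 84 = 30,660) | 17.5% |
| 365 days | 5,373 / (365 × 365 = 133,225) | 4.03% |
| 400 days | 5,373 / (365 × 400 = 146,000) | 3.68% |

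Leaving out onsets on the dosing day gives 72%, 46% and 16% for the first three rows and 3.4% over 400 days.

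**Day and month missing.** Every onset in the rest of the calendar year of first dose is lost: 365 × 364 / 2 = 66,430. Shares: 66,430 / 133,225 = 49.9% (365 days) and 66,430 / 146,000 = 45.5% (400 days).

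**Scaling to all AEs.** The rate of incomplete dates is not in the documents. If 1% to 10% of AEs lacked the day (assumed):
- all post-dose AEs: 3.7% × 1% to 10% = 0.04% to 0.4%;
- AEs in the first 30 days: 49% × 1% to 10% = 0.5% to 4.9%.

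**Cost of a floor at first dose.** Take screening AEs with the day missing and onset uniform over the 28 days before dosing: 365 × 28 = 10,220 pairs. Those in the same month as first dose number min(28, k - 1) for each k: 462, 434 and 378 per month, in total 7 × 462 + 4 × 434 + 378 = 5,348, or 52.3%. With a fully known stop date, the AE must also last to first dose. For a duration of D days counted from onset, the term becomes min(D - 1, k - 1):
- D = 3: 694 / 10,220 = 6.8%
- D = 7: 1,938 / 10,220 = 19.0%
- D = 14: 3,653 / 10,220 = 35.7%

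**The case against.** The best defence is the wording of SAP 3.1.8. The 1st-of-month rule is introduced as an example under a conservative principle, and for treatment-emergent status that principle points to the first-dose date. SAP 7 also mentions separate programming specifications, not available here, which might contain a floor or a TEAE window. Both are possible. But the only written instruction does the reverse, and the SAP does not refer to the specifications for this point. Two programmers could follow the text in good faith and obtain different TEAE counts.

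The start of the TEAE window can reasonably be inferred from Day 1 and from the definition of concomitant medication, so the missing definition alone would be a small gap.

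On size, much of the objection stands. The rate of incomplete dates is assumed. Scheduled visits often bound an onset to a few months, so a missing month should be uncommon. Serious AEs are reported within 24 hours of knowledge and should be better dated. Laboratory-based ESIs use test results, and the ESI overview is not limited to TEAEs. Safety is descriptive only. Protocol 10.1.5 adds that "Data identified as erroneous, or data that are missing, will be referred to the study site for resolution through data queries", and SAP 7 that "All available data will be presented in subject data listings". SAP 3.1.8 also lists dates as collected. These safeguards reduce the number of cases and keep them visible, but they do not restore them to the counts in SAP 3.5.1.

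**Conclusion.** The concern holds. Followed as written, SAP 3.1.8 can date a post-dose AE before Day 1 and, under the usual TEAE definition, remove it from the SAP 3.5.1 tables, against the section's own aim. The overall effect is probably small: 0.04% to 0.4% of post-dose AEs if 1% to 10% lack the day. It is larger early, at 0.5% to 4.9% of those in the first 30 days. Those figures rest on uniform first-dose dates and onsets, the assumed TEAE definition and the assumed rate of incomplete dates. The rule does not differ by arm, so this is undercounting and not a between-arm bias. No efficacy result, power or error rate is affected. It should be corrected before unblinding because the rule is wrong for AE starts and the correction is cheap.

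**What to change.** - **SAP 3.5.1:** define a TEAE as an AE with onset, or worsening, on or after the first dose of study drug, and state where the window ends. AE collection already runs to the EOS Visit, which gives a natural end.
- **SAP 3.1.8, AE start dates only:** if the known parts of the start date are compatible with onset on or after first dose, and the stop date is not before first dose, impute the later of the first-dose date and the earliest date compatible with the known parts. Judge the stop date after stop-date imputation, with an ongoing event or missing stop date counted as not before first dose. Treat a wholly missing start date the same way, which gives the first-dose date. In all other cases impute the earliest date compatible with the known parts, or the consent date if the start is wholly missing.
- Keep the present rule for medical history and medication starts.

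With this rule no post-dose AE is moved before Day 1 by imputation, and partial dates in later months or years are unchanged.

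The work is two short SAP edits and a few lines of ADaM code. The price is that some screening AEs become treatment-emergent in both arms: 52% of those with the day missing if the stop date is also partial or missing, and 7%, 19% or 36% with a known stop date and assumed durations of 3, 7 or 14 days. That adds some noise to the arm comparison, but it errs toward counting events.

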3.1.9 Laboratory Values Above or Below Limits of Quantification

For continuous laboratory values less than the lower limit of quantification (LLQ), half of the lower limit value (i.e., LLQ/2) will be used in the analysis. For values greater than the upper limit of quantification (ULQ), the upper limit value (i.e., ULQ) will be used in the analyses.

3.1.10 Discrepancies Between Interactive Response Technology (IRT) and eCRF Stratification Variables

Summary tables by treatment group for stratification variables (CV risk and Baseline statin dose) will be provided to show any discrepancies between what was reported through IRT vs data collected in the study eCRF. The stratification variables based on data collected in the eCRF will be defined as follows:

- HIS includes atorvastatin 40 or 80 mg, rosuvastatin 20 or 40 mg. Participants will be defined as having HIS treatment based on the data collected in the eCRF and if any following were used at baseline: average daily dose of atorvastatin \geq 40 mg or average daily dose of rosuvastatin of \geq 20 mg. For Japan only, HIS includes atorvastatin 10 or 20 mg for non-familial hypercholesterolemia, atorvastatin 20 or 40 mg for heterozygous familial hypercholesterolemia, and rosuvastatin 10 or 20 mg. Participants will be defined as having HIS treatment, for Japan only, if any following were used at baseline: average daily dose of atorvastatin \geq 10 mg or average daily dose of rosuvastatin of \geq 10 mg. Participants having other doses of statin or other statin treatment, or no statin will be defined as non-HIS therapy.
- Participants will be defined as having CV risk (HeFH, non-HeFH) based on the CV history collected in the eCRF.

3.1.11 Handling of Duplicate Enrollment

The list of confirmed duplicate participants will be directly incorporated into Analysis Data Model (ADaM) dataset as a variable to identify a duplicate participant. Duplicate participants will be excluded from all analysis.

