#### 9 STATISTICS

## 9.1 Analysis Populations

The Intent-to-Treat (ITT) Population will include all participants who are randomized into the study. Treatment classification will be based on the randomized treatment.

The Full Analysis Set (FAS) will include all participants who are randomized into the study, take any study drug, and have at least 1 post-treatment lipid data assessment. Treatment classification will be based on the randomized treatment.

The Modified ITT (mITT) Population will include all randomized participants who receive at least 1 dose of any study drug and have data for both the Day 1 and Day 84 LDL-C assessments. Treatment classification will be based on the randomized treatment.

The Per-Protocol (PP) Population will include all participants in the mITT Population who did not experience a major protocol deviation that potentially impacted the primary efficacy endpoint. The PP Population, along with the reason for exclusion, will be finalized prior to study unblinding.

The Safety Population will include all participants who receive at least 1 dose of any study drug. Treatment classification will be based on the actual treatment received. The Safety Population will be the primary population used for the safety analyses.

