3.2 Analysis Populations

3.2.1 Intent-to-Treat (ITT) Population

The ITT Population will include all participants who are randomized into the study. Treatment classification will be based on the randomized treatment.

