3.2.2 The Full Analysis Set (FAS)

The FAS will include all participants who are randomized into the study, take any study drug, and have at least 1 post-treatment lipid data assessment. Treatment classification will be based on the randomized treatment.

3.2.3 *Modified Intent-to-Treat (mITT) Population*

The mITT Population will include all randomized participants who receive at least 1 dose of any study drug and have data for both the Day 1 and Day 84 LDL-C assessments. Treatment classification will be based on the randomized treatment.

3.2.4 *Modified Intent-to-Treat (mITT) On-Treatment Population*

The mITT On-Treatment Population will include all randomized participants who, have data for both the Day 1 and Day 84 LDL-C assessments. Participants in the obicetrapib group with PK values less than 3 standard deviations from the mean obicetrapib concentration should be excluded. Treatment classification will be based on the randomized treatment.

Rationale: in previous studies, such as ROSE (protocol number TA-8995-201) and TULIP (protocol number TA-8995-03), and ROSE2 (protocol number TA-8995-202), it was demonstrated that the minimally observed obicetrapib concentration for C_{max} was less than three standard deviations from the mean at respectively Week 4 and Week 12 [3-5].

3.2.5 *Per-Protocol (PP) Population*

The PP Population will include all participants in the mITT Population who did not experience a major protocol deviation that potentially impacted the primary efficacy endpoint. The PP Population, along with the reason for exclusion, will be finalized prior to study unblinding.

3.2.6 *Safety Population*

The Safety Population will include all participants who receive at least 1 dose of any study drug. Treatment classification will be based on the actual treatment received. The Safety Population will be the primary population used for the safety analyses.

3.2.7 *24-hours ABPM Population*

The 24-hour ABPM Population will include all participants in the ITT Population who received at least 1 dose of any study drug and have valid data for both the baseline and Day 270 24-hour ABPM assessments and have 80% to 120% treatment compliance.

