3.4 Efficacy Assessment

The ITT Population will be the primary population for the efficacy analysis. Efficacy will also be analyzed using the FAS, mITT Population, mITT On-Treatment Population, and PP Population as supportive analyses.

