3.4.1 Primary Efficacy Endpoints

Primary Analysis

The primary efficacy endpoint is the percentage change from Baseline to Day 84 in LDL-C in the obicetrapib group compared to placebo group.

The LDL-C values measured by preparative ultracentrifugation (PUC) will be used. If the later is not available, the LDL-C values will be assumed missing.

All the analysis for primary efficacy endpoint will be repeated with LDL-C values calculated as follows:

1. LDL-C will be calculated using the Friedewald equation unless triglycerides ≥ 400 mg/dL or LDL-C ≤ 50 mg/dL; where, LDL-C level will be measured directly by PUC.
2. LDL-C will be calculated using the Martin-Hopkins equation unless triglycerides ≥ 400 mg/dL or LDL-C ≤ 50 mg/dL; where, LDL-C level will be measured directly by PUC.

Primary Estimand

To assess the primary efficacy endpoint, the primary estimand is defined by the following key attributes:

- **Treatment:** obicetrapib versus placebo
- **Target Population:** participants who are randomized into the study
- **Analysis Population:** The ITT Population
- **Intercurrent events:** treatment discontinuation, prohibited medication use
- **Analysis set and handling of intercurrent events:** Treatment policy strategy will be used. All available values of LDL-C at Baseline and Day 84 will be included in the calculation of the percentage change from Baseline to Day 84.
- **Population level summary:** The difference in LS mean percentage change in LDL-C from Baseline to Day 84 between treatment groups

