6 CHANGES FROM PROTOCOL-SPECIFIED STATISTICAL ANALYSES

There have been three changes from the protocol v6.0.

The first change is the addition of time points to the exploratory endpoint, Day 84 and Day 180, to evaluate trough levels of obicetrapib from Baseline.

The second change relates to the effect of obicetrapib on cardiovascular events. Additional exploratory endpoints were added:

- The time from Randomization until the first confirmed occurrence of a composite of CV death, non-fatal MI, or non-fatal stroke, or coronary revascularization
- The time from Randomization until the first confirmed occurrence of a composite of CHD death, non-fatal MI, or non-fatal stroke, or non-elective coronary revascularization
- The time from Randomization until the first confirmed occurrence of a composite of CHD death, non-fatal MI, or non-fatal stroke, or coronary revascularization
- The time from Randomization until the first confirmed occurrence of a composite of CHD death, non-fatal MI, or non-fatal stroke
- MALE events
- Number of total CV events.

The third change is the inclusion of subgroup analysis.

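### The SAP removes undefined duplicate participants from every analysis, which contradicts its own ITT and Safety definitions and leaves events after dosing out of the safety summaries

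*SAP*

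**What the plan says.** SAP 3.1.11 provides that the list of confirmed duplicates will be "directly incorporated into Analysis Data Model (ADaM) dataset as a variable to identify a duplicate participant", and then: "Duplicate participants will be excluded from all analysis". The section does not define a duplicate, does not say which enrolment carries the flag, and makes no separate provision for safety data.

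The population definitions have no matching exception. SAP 3.2.1: "The ITT Population will include all participants who are randomized into the study". SAP 3.2.6: "The Safety Population will include all participants who receive at least 1 dose of any study drug", classified by the treatment actually received. Protocol 9.1 agrees: "The Intent-to-Treat (ITT) Population will include all participants who are randomized into the study". SAP 3.4 adds: "The ITT Population will be the primary population for the efficacy analysis". In SAP 3.4.1 the target population of the primary estimand is "participants who are randomized into the study".

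The protocol has no rule for duplicates. SAP section 6 opens: "There have been three changes from the protocol v6.0". The three are added trough time points, added cardiovascular endpoints and subgroup analyses.

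**The concern.** A person who was randomised, took study drug and was later confirmed as a duplicate belongs to ITT and Safety under SAP 3.2 and to no analysis under SAP 3.1.11. Two programmers working from the same SAP could build different populations. If the general rule prevails, it is a post-randomisation exclusion from the primary population that the protocol does not foresee and section 6 does not declare.

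The safety side matters more. An exclusion from every analysis covers the tables of adverse events, serious events, deaths and events of special interest. Someone whose enrolments overlapped may have taken two supplies, possibly one of each product. A safety summary should account for that exposure.

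**Working it through.** **1. The texts side by side.** Take one person with two randomisation numbers, dosed under both.

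| Question | SAP 3.2, protocol 9.1 | SAP 3.1.11, duplicate = person | SAP 3.1.11, duplicate = later enrolment |
|---|---|---|---|
| First enrolment in ITT? | Yes | No | Yes |
| Events after dosing, first enrolment, in safety tables? | Yes | No | Yes |
| Events after dosing, later enrolment, in safety tables? | Yes | No | No |

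Both readings of 3.1.11 conflict with the Safety definition in the last row. The reading by person also conflicts with ITT. For someone who took both products, SAP 3.2.6 does not say what the actual treatment is. SAP 3.3.3 tabulates reasons for exclusion only for the Per-Protocol Population, so it would not show how many duplicates were removed from ITT or Safety, or from which arm.

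**2. The plan's own figures** (SAP 2.2.2, protocol 9.2.6): 2400 randomised 2:1, 5% dropout, difference 30 points, SD 15, one-sided 0.025.

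- Evaluable: 2400 × 0.95 = 2280, or 1520 and 760.
- SE = 15 × √(1/1520 + 1/760) = 0.666 points.
- 30 / 0.666 = 45 standard errors, so power is 1.000, consistent with the stated figure of more than 90%.

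**3. Size under assumed duplicate rates.** The documents give no count, so the rate d is an assumption, taken from 0.1% to 5% of 2400. Formulas:

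- People removed = 2400d; in the obicetrapib arm m = 2400d × 2/3.
- SE = 0.6664 / √(1 − d).
- Shift in the estimate if those removed had no treatment effect at all (a deliberate extreme) = 30d.
- Chance that at least one affected obicetrapib-arm person leaves the tables, for an event with incidence r: 1 − (1 − r)^m. This assumes independence and the same incidence as in other participants.

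| d | People | m | SE (points) | Shift (points) | Chance, r = 1% | Chance, r = 5% |
|---|---|---|---|---|---|---|
| 0.1% | 2.4 | 1.6 | 0.667 | 0.03 | 1.6% | 7.9% |
| 0.5% | 12 | 8 | 0.668 | 0.15 | 7.7% | 34% |
| 1% | 24 | 16 | 0.670 | 0.30 | 15% | 56% |
| 5% | 120 | 80 | 0.684 | 1.50 | 55% | 98% |

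Power is 1.000 in every row, and the SE rises by at most 0.684 / 0.666 − 1, about 2.6%. The table counts one randomised place per person. If each person held two and both were removed, 5% of people would mean 10% of places and an SE of 0.6664 / √0.90 = 0.702, which is still negligible against 30.

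**The case against.** Four points deserve weight.

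- **The term is ambiguous.** Participants are tracked by number, and protocol 4.5 gives a rescreened person a new one. A duplicate participant may therefore mean only the surplus enrolment. A reader might infer that valid first-enrolment data are certain to be discarded. The documents do not establish that; it is the plain reading, not the only one. The ambiguity is itself part of the problem.
- **The events are not deleted.** A reader might infer that serious events or deaths in duplicates vanish. The SAP adds a flag; it does not remove records. SAEs are reported within 24 hours (protocol 8.4), overdose and misuse have their own reports (8.7), the DSMB reviews unblinded safety data (9.2.5) and the CEC adjudicates all deaths (9.2.4). SAP section 7 plans listings of all available data, though whether the exclusion extends to listings is not stated. What is lost is the entry in summary tables and rates.
- **Selective removal is constrained.** Under SAP 5.2, population exclusions are finalised before unblinding. The documents do not support an inference that duplicates could be removed with knowledge of treatment. The safeguard does not resolve the contradiction or restore the safety counts.
- **First-enrolment data may be contaminated.** With overlapping enrolments, a person may have taken both products, and exclusion criteria 14 and 15 bear on repeat entry. That supports a sensitivity analysis without duplicates. It does not by itself cancel the first assignment, and an estimand using a treatment policy strategy for all randomised participants is not defined by clean exposure.

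**Conclusion.** The inconsistency stands. SAP 3.1.11 cannot be applied together with SAP 3.2, protocol 9.1 and the primary estimand, and section 6 does not declare it as a departure. It should be corrected before database lock.

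The primary conclusion is not at risk. At any rate in the assumed range, power and precision barely change, and even the extreme no-effect case at 5% duplicates moves the estimate by 1.5 points out of 30. The consequence that matters is incomplete safety summaries. At an assumed 1% of duplicates, with the whole person removed, there is a 15% chance of omitting at least one obicetrapib-arm case of an event with 1% incidence, and a 56% chance at 5% incidence. These figures depend on an unknown count, which may be zero.

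**What to change.** - In SAP 3.1.11, define a duplicate at record level: two or more enrolments confirmed to belong to one person, with the first randomisation by date as the index record and the others flagged.
- Keep the index randomisation in ITT under its assigned arm. Exclude only later enrolments from efficacy.
- Keep every dosed person in the Safety Population, counted once, classified by actual treatment received, with events from all enrolments included. Pre-specify the classification of anyone who received both products, for example summarised with obicetrapib and listed separately.
- Cross-reference the rule in SAP 3.2 and declare it in section 6.
- Report the number of duplicates by arm.
- Add a sensitivity analysis of the primary endpoint that excludes all duplicates.

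The cost is SAP wording, a record-level flag and a small amount of programming. The downside is that a few first-enrolment values may be contaminated by overlapping use; the sensitivity analysis shows whether that matters.
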